4.6.7.2. Hypersensitivity Events

Hypersensitivity reactions and related information reported in eCRF will be listed and summarized by treatment.

Summaries of all potential hypersensitivity reactions will be generated by PT with decreasing frequency by treatment. The AE database will be searched using predefined SMQs to identify events consistent with hypersensitivity events. Detailed search criteria can be found in Appendix 6 (Section 6.6).

4.6.7.3. Major Adverse Cardiovascular Events

Death and nonfatal cardiovascular AEs (NCAEs) will be adjudicated by a committee of physicians external to Lilly with cardiology expertise. This committee will be blinded to treatment assignment.

The NCAEs to be adjudicated include:

- myocardial infarction
- cardiogenic shock
- hospitalization for unstable angina
- hospitalization for heart failure
- coronary interventions (such as coronary artery bypass graft or percutaneous coronary intervention)
- resuscitated sudden death,
- cerebrovascular events, including cerebrovascular accident (stroke) and transient ischemic attack,
- peripheral revascularization procedure, and
- peripheral arterial event

The counts and percentages of participants with adjudicated NCAEs may be summarized by treatment.

In addition, NCAEs reported by investigator may also be summarized. Death reported by investigator may be listed in a separate table.

A listing of participants reporting NCAEs, either reported by an investigator or identified by the clinical endpoint committee (CEC), will be provided. This listing will include treatment, participant identification including the site number, date of event, type of event as reported by the investigator, type of event as adjudicated by the CEC, time from first dose of study drug to the event, and time from last dose to the event (if participant has discontinued study drug prior to the event).

4.7. Other Analyses

Subgroup analyses of the primary endpoint will be conducted to assess the consistency of the intervention effect across the following subgroups:

- age group (<65 vs. \geq 65 years old)
- race (white, non-white)
- gender: female versus male
- ethnicity
- baseline body mass index (BMI) (kg/m^2) (< median vs. \geq median)
- baseline Lp(a) level (<275 nmol/L vs. \geq 275 nmol/L)
- baseline eGFR(<60 and \geq 60 mL/min/1.73 m²)
- diabetic vs non-diabetic.

For each subgroup analysis, the following model will be conducted:

• Percent change in Lp(a) from baseline to Week 12.

For the purposes of the subgroup analysis, diabetic status will be defined using the criteria described in Appendix 7 (Section 6.7).

If the number of participants is too small (less than 10%) within a subgroup, then the subgroup categories may be redefined prior to unblinding the study or descriptive statistical analysis will be applied.

Additional subgroup analyses may be performed. For example, subgroup analyses may be done for Chinese and Japanese populations, respectively, to support local regulatory interactions.

4.8. Interim Analyses

A planned interim analysis will be conducted when at least 50% enrollment has been completed. The interim analysis will consist of a subset of the primary efficacy estimand analyses specified in the SAP for the primary endpoint, such as the descriptive summaries described in Section 4.1, the MMRM model described in Section 4.1.2.1, and the Bayesian dose-response model described in Section 4.5.1.

Additionally, a planned interim analysis may be conducted when at least 50% of the participants complete Week 12 at Visit 7 or discontinue the study. The details regarding the number of participants and type of analysis will be provided in the assessment committee (AC) charter and in the unblinding plan.

All interims will be for the purpose of internal planning and decision-making and may assess safety, PK, and/or efficacy measures. Additional details related to statistical methods will be described in the SAP. An assessment committee (AC) will be formed to review the interim analyses in an unblinded manner. Only blinded study team members will have contact with the sites. Information that may unblind the study during the analyses will not be reported to study sites or blinded study team members before the study has been unblinded. Study sites will receive information about interim results only if deemed necessary for the safety of the participants. The study will not be stopped based on the efficacy of LY3473329 versus placebo. Therefore, there will be no inflation of the type 1 error rate, and no need to employ an alpha spending function or multiplicity adjustment.

The database lock and primary data analysis for Study EKBC may occur when all participants have completed the study. Unblinded data and results will not be shared with the study sites to maintain blinding at the sites while the study is still ongoing. Details will be specified in the blinding or unblinding plan.

4.9. Changes to Protocol-Planned Analyses

There are no changes to the analyses described in the protocol.

5. Sample Size Determination

The sample size calculation is based on the primary efficacy estimand and its endpoint, percent change from baseline at Week 12 in Lp(a).

Approximately 233 participants will be randomly assigned in a 1:2:2:2 ratio to LY3473329 10 mg:60 mg:240 mg:placebo. Assuming a 10% dropout rate, this results in approximately 30 completers for the 10-mg group and 60 completers per arm for the rest of the groups.

Assuming a standard deviation of 20% and a 2-sided alpha level of 0.05, the completers for each treatment arm will provide >99% power to detect a treatment difference of 60% reduction for the primary endpoint of LY3473329 verses placebo. The sample size was determined appropriate to provide a sufficient amount of safety data.

6. Supporting Documentation

6.1. Appendix 1: Demographic and Baseline Characteristics

A listing of participant demographics for all randomized participants will be provided. All demographic and baseline clinical characteristics will be summarized by treatment groups for all randomized participants.

Baseline demographic and clinical characteristics of special interest include but are not limited to: age (years), sex (female, male), race, ethnicity, height (cm), weight (kg), BMI (kg/m²), age group (<65 years, \geq 65 years), Lp(a) measured by apo(a) assay, Lp(a) measured by intact Lp(a) assay, plasminogen, LDL-C, ApoB, hsCRP, total cholesterol, HDL-C, triglycerides, baseline Lp(a) strata by apo(a) assay, eGFR (CKD-EPI, mL/min/1.73m²), and eGFR groups (<30, \geq 30 to <45, \geq 45 to <60, \geq 60 to <90, and \geq 90 mL/min/1.73 m²).

6.2. Appendix 2: Historical Illnesses and Pre-existing Conditions

The count and percentages of participants with historical illnesses and pre-existing conditions will be summarized by treatment groups using the MedDRA PTs nested within SOC. The SOC will be in alphabetical order. Conditions (that is, PTs) will be ordered by decreasing frequency within SOC. This will be summarized for all randomized participants.

6.3. Appendix 3: Treatment Compliance

Listing and summary of discontinuing study treatment (including discontinuation reason) and discontinuing study will be provided by treatment groups.

If data warrant, counts and percentages of participants who have missed tablets of study drug (eCRF data) \geq 7 days will be summarized for each treatment group. Listings of such participants will also be provided. Additionally, non-compliance, defined as having \geq 75% of missed tablets before permanent study drug discontinuation, will be summarized by treatment group.

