6.1. Study Intervention(s) Administered

All participants will be required to take 4 tablets by mouth every day for 12 weeks to ensure blinding.

	Arm A	Arm B	Arm C	Arm D
Intervention Name	LY3473329 and placebo	LY3473329 and placebo	LY3473329	Placebo
Dose Formulation	Tablet	Tablet	Tablet	Tablet
Dosage Levels				
LY3473329	10 mg (1 tablet, 10 mg)	60 mg (1 tablet, 60 mg)	240 mg (4 tablets, 60 mg)	0 tablets
Placebo	3 tablets	3 tablets	0 tablets	4 tablets
Frequency	QD	QD	QD	QD
Route of Administration	РО	РО	РО	РО
Authorized as defined by EU Clinical Trial Regulation	Not authorized in EU	Not authorized in EU	Not authorized in EU	Not authorized in EU

Abbreviations: EU = European Union; PO = by mouth; QD = once daily.

LY3473329 and placebo tablets will be taken orally with approximately 240 mL of water at approximately the same time, preferably in the morning, each dosing day. On specific visit days, participants will be required to not take the drug at home and follow directions provided by the site on when to take the drug after they arrive at the clinical site.

Participants should be trained to get one pill from each bottle and should do this themselves at Visit 2 under supervision.

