6.4. Study Intervention Compliance

When participants self-administer study intervention(s) at home, compliance with study intervention will be assessed at each visit. Compliance will be assessed by direct questioning and counting returned tablets and documented in the source documents and case report form (CRF).

A record of the number of study intervention tablets dispensed to and taken by each participant must be maintained and reconciled with study intervention and compliance records. Intervention start and stop dates, including dates for intervention delays, will also be recorded in the CRF.

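### SAP 6.3 calls a participant non-compliant only when at least 75% of tablets were missed, so the non-compliance rate by arm says almost nothing about adherence

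*SAP*

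**What the plan says.** SAP 6.3 (Appendix 3: Treatment Compliance) plans two tablet-level summaries.

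- **Missed days.** The first is conditional: "If data warrant, counts and percentages of participants who have missed tablets of study drug (eCRF data", with the bar at 7 days or more, by treatment group. It adds: "Listings of such participants will also be provided".
- **Non-compliance.** The second labels a participant non-compliant at or above 75% "of missed tablets before permanent study drug discontinuation", again by treatment group.

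Only non-compliance is defined. The SAP plans no category called compliant.

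The dosing denominator is in Protocol 6.1: "All participants will be required to take 4 tablets by mouth every day for 12 weeks to ensure blinding". Protocol 6.4 says how the data arise: "Compliance will be assessed by direct questioning and counting returned tablets", with results recorded in the CRF. It also requires a record of tablets dispensed and taken.

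Two other places bear on the use of the result. SAP 1.1 sets the primary estimand as the effect under adherence to randomized treatment. SAP Section 3 removes data from the EAS only after study drug is discontinued or an Lp(a) modifying medication is started.

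**The concern.** A non-compliance rate should separate arms in which participants took most of their tablets from arms in which they did not. A threshold of 75% missed does this only for participants who have almost stopped dosing without being recorded as discontinued. The preceding sentence of SAP 6.3 treats 7 missed days as worth counting and listing, so the two thresholds in one paragraph sit far apart. The natural explanation is that taken and missed were exchanged.

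What is at stake is interpretation. Doses missed while a participant is nominally on drug do not trigger exclusion from the EAS, so those data enter the MMRM of SAP 4.1.2.1 under an estimand that assumes adherence. In a dose-finding trial, partial adherence in one arm can look like a weaker dose. A reader of the study report would turn to the adherence tables to judge that, and a non-compliance rate near zero would give false reassurance. Exposure in SAP 4.6.1 does not fill the gap: it is the last dose date minus the first dose date plus 1, so scattered missed days leave it close to 84.

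**Working it through.** The plan gives a cut-off and no derived figure, so the check is to see what the cut-off means in tablets and days.

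**Inputs.** 4 tablets daily for 12 weeks (Protocol 6.1); cut-offs of 75% missed and 7 days missed (SAP 6.3); Visit 7 window of ±4 days (Protocol 1.3).

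**Denominator.** 12 × 7 = 84 days; 84 × 4 = 336 tablets.

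**Where the flag starts.** 0.75 × 336 = 252 tablets; 252 / 4 = 63 whole days.

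**Largest shortfall not counted, in whole days.** 62 / 84 = 248 / 336 = 73.8% missed. Doses taken: 84 − 62 = 22, and 22 / 84 = 26.2%.

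**Sensitivity to the visit window.**

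| Treatment days | First flagged | Largest unflagged | Share missed |
|---|---|---|---|
| 80 | 60 | 59 | 73.75% |
| 84 | 63 | 62 | 73.8% |
| 88 | 66 | 65 | 73.9% |

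**What the rate would show.** If every participant in an arm missed half the tablets, each would miss 168 of 336 = 50%, below 75%. The arm's non-compliance rate would be 0%.

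**Comparison with the other rule.** 7 / 84 = 8.3%. The non-compliance bar is 63 / 7 = 9 times as high. Participants with 7 to 62 missed days can appear only in the conditional summary and listing.

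**Does the 7-day rule catch the 62-day case?** On a cumulative reading, yes, because 62 is at least 7. The SAP does not say whether days are cumulative or consecutive, or whether one missed tablet makes a missed day. With 22 dosed days there can be up to 23 separate runs of missed days, averaging 62 / 23 = 2.7 days. On a consecutive reading, this participant could escape the 7-day rule as well.

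**The reversed rule.** Less than 75% taken means more than 25% missed. 84 / 336 is exactly 25.0% and is not flagged; 85 / 336 = 25.3% is. In whole days, 21 is exactly 25.0% and 22 / 84 = 26.2%, so the flag starts at 22 days instead of 63.

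**The case against.** The strongest reply is that SAP 6.3 does not rest on this flag alone. The same section counts and lists participants with 7 or more missed days, and the 62-day participant passes that bar easily on a cumulative reading. The 75% category is introduced as an addition and may be a deliberate extreme class. Adherence is also assessed at Visits 3 to 7 by questioning and tablet counts, and a dosing log is reviewed. Plasma concentrations are sampled at several visits (Protocol 1.3 and 8.4) and measure active drug directly. Finally, no analysis set, model or decision rule uses the flag.

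Most of this stands, and it limits the point. A reader might infer that the plan cannot detect poor adherence, or that this table is its only check on dosing. The 7-day output, the tablet counts and the concentrations show otherwise. Nor is the 62-day participant reported as compliant; that participant is simply not counted as non-compliant.

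A reader might also infer from "Participants should be trained to get one pill from each bottle" that someone could skip only the bottle holding the active tablet in Arms A or B and go unseen. The documents do not say how tablets are allotted to bottles or that counts are kept by bottle. A person skipping one tablet of four each day would have missed tablets on all 84 days, which a plain reading of the 7-day rule could catch. That person misses exactly 25% of tablets, so a rule of more than 25% missed would not flag the case either. The bottle argument adds no support here.

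The reply does not rescue the non-compliance rate itself. The 7-day summary is conditional and leaves a missed day undefined. If it is not produced, the 75% flag is the only tablet-level summary left in the section. Sparse concentrations mainly reflect recent dosing.

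**Conclusion.** The point holds as a defect in a descriptive definition. Non-compliance as written starts at 252 of 336 tablets, or 63 of 84 days, and leaves out participants who took as little as 26.2% of their daily doses. The by-arm rate will therefore be near zero almost regardless of adherence.

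This rests on three assumptions:

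- The figures apply to a participant with 84 treatment days. The boundary barely moves at 80 or 88.
- The expectation of a near-zero rate assumes that few participants miss three quarters of their tablets while still on study drug. The documents give no adherence distribution.
- The threshold is read literally. A reader might conclude that its direction is certainly inverted. That is likely given the 7-day rule beside it, but neither document states another intention.

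The consequence is confined to interpreting an estimand premised on adherence. The EAS, the primary model, the estimates and the p-values are unaffected. The change is worth making because it is cheap and the data are already collected.

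**What to change.** In SAP 6.3:

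1. Define non-compliance as taking less than 75% of planned tablets before permanent discontinuation of study drug. That is more than 25% missed: over a full 12 weeks, 85 or more of 336 tablets, or 22 or more whole days. The 75% is the SAP's own figure with the direction reversed, so the sponsor should confirm that this was meant. If the extreme class was intended, it can stay as a separately labelled line.
2. Remove the condition on the 7-day summary and listing and state that days are cumulative. Alternatively, provide an unconditional by-arm summary of the percentage of planned tablets taken.
3. If the 7-day output is kept, say whether one missed tablet or all four make a missed day.

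The cost is a few sentences in the SAP and one derived variable from tablet counts that Protocol 6.4 already requires. The downside is a less favourable reported compliance rate.

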6.4. Appendix 4: Concomitant Medications

Concomitant medications will be summarized by treatment group. The percentages of participants who took concomitant medication will be summarized by treatment using PTs nested within Anatomical Therapeutic Chemical (ATC) Level 3 codes. The concomitant medications will be ordered by decreasing frequency within each ATC level.

6.5. Appendix 5: Important Protocol Deviations

Important protocol deviations are identified in the Trial Issues Management Plan. A listing and summary of important protocol deviations by treatment groups will be provided at the end of study (for all randomized participants).

6.6. Appendix 6: Searching Criteria for Additional Safety Assessments

Hepatic Treatment-Emergent Adverse Events

Treatment-emergent potentially drug-related hepatic disorders will be summarized by treatment using the MedDRA PTs contained in any of the following SMQs:

- Broad and narrow terms in the Liver related investigations, signs and symptoms SMQ (20000008)
- Broad and narrow terms in the Cholestasis and jaundice of hepatic origin SMQ (2000009)
- Broad and narrow terms in the Hepatitis non-infections SMQ (2000010)
- Broad and narrow terms in the Hepatic failure, fibrosis and cirrhosis and other liver damage SMQ (20000013), and
- Narrow terms in the Liver-related coagulation and bleeding disturbances SMQ (2000015).
- Narrow PTs in Gallbladder related disorders SMQ (2000124)
- Narrow PTs in Biliary tract disorders SMQ (20000125); and
- Narrow PTs in Gallstone related disorders SMQ (2000127).

Hypersensitivity Events

The hypersensitivity TEAE are characterized as follows:

- Narrow and algorithm terms in Anaphylactic reaction SMQ (2000021)
- Narrow terms in Angioedema SMQ (2000024)
- Narrow terms in Severe cutaneous adverse reactions SMQ (2000020)
- Narrow terms in Hypersensitivity SMQ (20000214), and
- Narrow terms in Vasculitis SMQ (20000174)

For the Anaphylactic reaction SMQ, the algorithmic query (per the MedDRA Maintenance and Support Services Organization SMQ guide) will be performed. An algorithmic case must include either:

- A narrow term from the SMQ (Category A of the SMQ);
- Multiple terms from the SMQ, from the same administration of study drug, comprising terms from at least 2 of the following categories from the SMQ:
 - Category B (Upper Airway/Respiratory)
 - Category C (Angioedema/Urticaria/Pruritus/Flush)
 - Category D (Cardiovascular/Hypotension)

The counts and percentages of participants who experienced a TEAE for the following will be analyzed:

- Any narrow or algorithm term from any 1 of the 5 SMQs indicated above (i.e., combined search across narrow and algorithmic portions of all 5 SMQs)
- Any narrow or algorithm term within each SMQ, separately (i.e., narrow SMQ search).

Within query, individual PTs that satisfied the queries will be summarized, and the Anaphylactic reaction SMQ algorithm will be summarized. A single event may satisfy multiple SMQs, in which case the event contributes to every applicable SMQ.

6.7. Appendix 7: Definition of Diabetic Status

For the purposes of the subgroup analysis on diabetic status, participants will be defined as diabetic if, prior to being randomly assigned, they possess ANY of

- baseline hemoglobin A1c levels greater than 6.5%
- concomitant medications classified as a *drug used in diabetes* according to the Anatomical Therapeutic Chemical (ATC) level 2 code A10.
- medical history classified under the MedDRA PT Diabetes Mellitus,
- medical history classified under the MedDRA LLT Diabetes Mellitus, or
- medical history of Type 2 Diabetes Mellitus reported on the clinical report form.

7. References

Signature Page for VV-CLIN-076972 v1.0

Signature Page for VV-CLIN-076972 v1.0

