5.2. Exclusion Criteria

Participants are excluded from the study if any of the following criteria apply:

Medical Conditions

9. Have a history or presence of an underlying disease, or surgical, physical, medical, or psychiatric condition that, in the opinion of the investigator, would potentially affect participant safety within the study or interfere with participating in or completing the study or with the interpretation of data.

10. Any of the following, or other events indicating unstable medical condition in the opinion of the investigator, within 3 months of Visit 1:

- a. major surgery
- b. coronary, carotid, or peripheral arterial revascularization
- c. stroke or transient ischemic attack
- d. myocardial infarction or unstable angina
- e. acute limb ischemia.
- 11. Have, in the 6 months prior to Visit 1, uncontrolled Type 1 or Type 2 diabetes, defined as an episode of ketoacidosis or hyperosmolar state requiring hospitalization, or have a hemoglobin A1c (HbA1c) ≥8% at Visit 1.
- 12. Have uncontrolled hypertension with a resting blood pressure ≥160 mm Hg systolic and/or ≥100 mm Hg diastolic at Visit 1; a repeat measure is allowed.
- 13. New York Health Association Class III or IV heart failure or last known left ventricular ejection fraction <30%.
- 14. Active or acute infection requiring systemic antiviral or antimicrobial therapy that will not be completed prior to Visit 2.
- 15. Malignancy within 5 years, except for basal or squamous cell carcinoma of the skin or carcinoma in situ of the cervix that has been successfully treated.
- 16. Recent history of, or current drug or alcohol abuse in the opinion of the investigator.
- 17. Have 2 or more clinically significant or severe drug allergies, or severe post-treatment hypersensitivity reactions, including, but not limited to
 - a. erythema multiforme major
 - b. linear immunoglobulin A dermatosis
 - c. toxic epidermal necrolysis
 - d. exfoliative dermatitis.
- 18. Hypersensitivity to the active substance or to any of the excipients.
- 19. Have a current infection with hepatitis B virus (HBV), that is, positive for hepatitis B surface antigen (HBsAg) and/or PCR positive for HBV deoxyribonucleic acid (DNA) (Section 8.2.5).
- 20. Have a current infection with hepatitis C virus (HCV), that is, positive for HCV ribonucleic acid (RNA) (Section 8.2.6).
- 21. Have human immunodeficiency virus (HIV) infection.

Prior/Concomitant therapy

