6.8. Concomitant Therapy

Any medication or vaccine, including OTC or prescription medicines, vitamins, and/or herbal supplements, that the participant is receiving at the time of enrollment or receives during the study must be recorded along with

- reason for use
- dates of administration including start and end dates, and
- dosage information including dose and frequency for concomitant therapy of special interest.

The medical monitor should be contacted if there are any questions regarding concomitant or prior therapy.

Participants on the following medications according to local practice must be on a stable regimen for at least 4 weeks prior to screening and expected to remain on a stable regimen through the end of the post-treatment follow-up period, unless changes need to be made because of AEs:

- lipid-lowering drugs (e.g., statins, ezetimibe, PCSK9 inhibitors, prescription-dose niacin, fibrates, fish oil, or other products containing omega-3 fatty acids, including OTC preparations), and
- testosterone, estrogens, progesterone, growth hormone, or progestins.

7. Discontinuation of Study Intervention and Participant Discontinuation/Withdrawal

Discontinuation of specific sites or of the study as a whole are handled as part of Appendix 10.1.

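### SAP Appendix 7 classes a participant as diabetic on any ATC A10 drug alone, whatever its recorded reason for use, so the diabetic subgroup of the primary endpoint may include participants without diabetes

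*SAP*

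**What the plan says.** SAP 4.7 lists eight subgroup factors, the last being diabetic versus non-diabetic, and gives their purpose: "Subgroup analyses of the primary endpoint will be conducted to assess the consistency of the intervention effect across the following subgroups". It adds that "diabetic status will be defined using the criteria described in Appendix 7".

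SAP Appendix 7 (section 6.7) then states that "participants will be defined as diabetic if, prior to being randomly assigned, they possess ANY of" five items:
- "baseline hemoglobin A1c levels greater than 6.5" (percent);
- "concomitant medications classified as a *drug used in diabetes* according to the Anatomical Therapeutic Chemical (ATC) level 2 code A10";
- medical history coded to the MedDRA preferred term for diabetes mellitus;
- medical history coded to the lowest level term of the same name;
- type 2 diabetes history on the case report form.

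Protocol 6.8 requires "reason for use" to be recorded for every medication that a participant is taking at enrolment or receives during the study. Appendix 7 does not refer to it.

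**The concern.** Under an any-of rule each item is sufficient alone. A normal HbA1c and no history of diabetes cannot override the A10 item, and the item does not ask why the drug is taken. Nothing in the plan picks up such cases later. SAP 4.7 allows subgroup categories to be redefined before unblinding only when a subgroup holds less than 10% of participants.

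At stake is how informative one consistency check is. Participants without diabetes in the diabetic group pull its estimate toward that of the non-diabetic group. The two then look more alike than they are, and likeness is what a consistency analysis is read for. The information that would prevent this is already to be recorded.

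**Working it through.** **The plan's own figure.** The plan gives no figure for diabetic status. The nearest one is the power statement in SAP section 5, which shows what is not affected.
- Completers: 233 × 1/7 × 0.9 = 30.0 on 10 mg, and 233 × 2/7 × 0.9 = 59.9 in each other arm. These match the stated 30 and 60.
- With SD 20 and a difference of 60, the standard error for 10 mg versus placebo is 20 × √(1/30 + 1/60) = 4.47. For 60 or 240 mg versus placebo it is 20 × √(2/60) = 3.65.
- The difference is about 13 and 16 standard errors, so power is 1.000 in both cases, in line with the stated >99%. Diabetic status does not enter this calculation, the primary model (SAP 4.1.2.1) or the superiority rule (SAP 4.3.2).

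**Share mislabelled.** Let p be the true proportion with diabetes and u the proportion of the others who take an A10 drug for another reason. Neither is in the documents. Both ranges are assumptions, and u may be zero.
- Mislabelled share of all participants = (1 − p)u
- Share of labelled diabetics who are not diabetic: m = (1 − p)u / [p + (1 − p)u]

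| p | u | (1 − p)u | of 233 | m |
|---|---|---|---|---|
| any | 0 | 0 | 0 | 0% |
| 0.5 | 0.05 | 0.025 | 5.8 | 0.025/0.525 = 4.8% |
| 0.3 | 0.05 | 0.035 | 8.2 | 0.035/0.335 = 10.4% |
| 0.5 | 0.20 | 0.100 | 23.3 | 0.100/0.600 = 16.7% |
| 0.3 | 0.20 | 0.140 | 32.6 | 0.140/0.440 = 31.8% |

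**Effect on the subgroup contrast.** Let D and N be the true treatment effects in diabetics and non-diabetics. Suppose that mislabelled participants respond like other non-diabetics and that the labelled non-diabetic group is pure.
- Labelled diabetic effect = (1 − m)D + mN
- Bias in that effect = m × gap, in the direction of N, where gap is the true difference D − N
- Apparent gap = (1 − m)(D − N)

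A true gap of 0 gives no bias at any m. A true gap of 10 points gives a bias of 1, 2 or 3 points at m = 10%, 20% or 30%. A gap of 20 points gives 2, 4 or 6 points.

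**Effect on an interaction test.** Take one of the two larger dose arms against placebo, with 60 completers per arm, SD 20 and the 2-sided interaction level of 0.10 in SAP 4.1. Assume that 40% are labelled diabetic and hold that share fixed, giving 24 diabetic and 36 non-diabetic participants per arm.
- SE = 20 × √(2/24 + 2/36) = 7.45
- Power ≈ Φ[(1 − m) × gap / 7.45 − 1.645]

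| True gap | m = 0 | m = 10% | m = 20% | m = 30% |
|---|---|---|---|---|
| 20 points | 85% | 78% | 69% | 59% |
| 10 points | 38% | 33% | 28% | 24% |

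These figures use the percent-scale SD from the sample size section, whereas the analysis itself is on the log scale. They show direction and order of size only.

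**The case against.** The strongest objection is that the documents give no evidence that anyone will be mislabelled. They describe A10 only as the class of drugs used in diabetes, name no member of it, and say nothing about its use without diabetes. Mild heart failure, reduced kidney function and high BMI are not excluded, but they are not qualifying conditions either. This stands in full against any claim that the subgroup is contaminated. What remains is that the rule as written would mislabel such a participant if one enrolled.

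A second objection is that an inclusive rule has a purpose. Protocol 5.2 excludes only those who "Have, in the 6 months prior to Visit 1, uncontrolled Type 1 or Type 2 diabetes", or who "have a hemoglobin A1c (HbA1c) ≥8% at Visit 1", so controlled type 1 diabetes may enter. The history items name only diabetes mellitus and type 2. A well-controlled type 1 participant coded to another term may be found through the A10 item alone. This is a good reason not to delete the item. It does not defend ignoring a recorded reason that is plainly not diabetes.

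A reader might also infer that the HbA1c cut adds to the problem. It does not. A strict inequality is narrower than an inclusive one, so it can only leave people out of the diabetic group, which is the opposite direction. All that is left is one boundary value, a reading of exactly 6.5% in someone who meets no other item.

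**Conclusion.** The point holds as a minor defect in a subgroup definition. The A10 item is sufficient alone and has no indication condition, although the reason for use is to be recorded.

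The number affected is unknown from the documents. Under the assumed ranges (30-50% truly diabetic, 0-20% of the rest on an A10 drug for another reason), 0 to about 33 of 233 participants would be mislabelled, and 0-32% of labelled diabetics would not be diabetic. The true gap would shrink by that same 0-32% only if mislabelled participants respond like other non-diabetics and the non-diabetic group is otherwise pure. If they respond differently, the direction of the bias is not fixed. If response does not differ by diabetic status or among those participants, there is no bias.

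A reader might infer that the primary result, or the entry limit on familial hypercholesterolemia and type 2 diabetes, is compromised. The documents do not support this. Appendix 7 serves one of eight consistency subgroups, while eligibility and the 40% limit follow the protocol's own entry criteria.

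**What to change.** Amend Appendix 7 before unblinding, and preferably before the first unblinded interim review in SAP 4.8:
- Keep the A10 item, but do not count a drug whose recorded reason for use is clearly something other than diabetes when no other listed item is met.
- Keep in the diabetic group anyone whose recorded reason is diabetes, missing or ambiguous. This protects participants with controlled type 1 diabetes who are identified only by their medication.
- Report how many participants are labelled diabetic by A10 alone, and how many were set aside under the new condition.
- State whether an HbA1c of exactly 6.5% counts as diabetic. This is a clarification, not part of the misclassification problem.

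The cost is a few lines of SAP text and a short blinded review of recorded indications for A10 drugs. No new data are needed, since Protocol 6.8 already requires the reason to be recorded. Some off-indication users with a missing or vague reason will stay mislabelled, and the reported A10-only count shows how many that could be at most.
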